- Receive and review SAE report forms from the study site and inform the sponsor of the SAE within 1 working day of the initial notification to Labcorp Drug Safety who will delete any information from the SAE report forms that may identify the subject.
- Write case narratives and enter the case into Labcorp's safety database as defined in the AE reporting plan.
- Produce appropriate reports of all suspected unexpected serious adverse reactions and forward them to the IRB/EC, Medicines and Healthcare Products Regulatory Agency, FDA, principal investigator, and the sponsor within the timeframes stipulated in the Clinical Trials Directive Guideline (ENTR/CT 3).

Appendix 5, Regulatory, Ethical, and Study Oversight Considerations, Data Quality Assurance, last bullet point

Previously read:

- Records and documents, including signed ICFs, pertaining to the conduct of this study must be retained by the investigator in the study site archive for at least 5 years after the end of the study unless local regulations or institutional policies require a longer retention period. No records may be destroyed during the retention period without the written approval of the sponsor. No records may be transferred to another location or party without written notification to the sponsor.

Now reads:

- Records and documents, including signed ICFs, pertaining to the conduct of this study must be retained by the investigator in the study site archive in accordance with 21 CFR 312.62(c) or for at least 5 years after the end of the study unless local regulations or institutional policies require a longer retention period. No records may be destroyed during the retention period without the written approval of the sponsor. No records may be transferred to another location or party without written notification to the sponsor.

Protocol

A Phase I, Multicenter, Randomized, Double-blind, Double-dummy, Placebo- and Positive-Controlled Study to Investigate the Effects of CBP-307 on the QTc Interval in Healthy Subjects

Protocol Amendment 3 Status: Final

Original Protocol Date: 18 March 2021

Protocol Amendment 1 Date: 10 May 2021

Protocol Amendment 2 Date: 03 August 2021

Protocol Amendment 3 Date: 26 October 2021

Protocol Version: 4.0

Investigational Medicinal Product: CBP-307

Protocol Reference Number: CBP-307AU002

Labcorp Study Number: 8463245

IND Number: 134585

Sponsor:

Connect Biopharma Australia Pty Ltd.
[name]
[name]
Hawthorn East, Victoria 3123
Australia

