During dose-titration period, 2 subjects (2 of 8 in Group C, 25%) experienced TEAEs. The TEAEs reported in Group C during the titration period included cough (12.5%) and increased upper airway secretion (12.5%). There were no TEAEs in the placebo group during this period.

During repeated-dose period, a total of 28 subjects (8 of 8 in Group A, 100%; 8 of 8 in Group B, 100%; 8 of 8 in Group C, 100%; and 4 of 6 in placebo group, 66.7%) experienced AEs. The most frequent TEAE in Group A was upper respiratory tract infection (37.5%) compared with placebo group; the most frequent TEAEs in Group B and Group C included decreased lymphocyte count (Group B, 87.5%; Group C, 100.0%), WBC count (Group B, 87.5%; Group C, 62.5%), and neutrophil count (Group B, 50%; Group C, 12.5%). The TEAEs noted in Group B during the repeated-dose period also included increased alanine aminotransferase (25%), gamma-glutamyltransferase (37.5%), and aspartate aminotransferase (12.5%), upper respiratory tract infection (12.5%), influenza (12.5%), chest pain (12.5%), lethargy (25%), and neck pain (12.5%); TEAEs in Group C during the repeated-dose period also included increased alanine aminotransferase (25%), decreased HR (12.5%), and mouth ulcer (12.5%); the TEAEs in placebo group included increased transaminase (16.7%), prolonged activated partial thromboplastin time (1/6, 16.7%), decreased hemoglobin (16.7%), upper respiratory tract infection (16.7%), diarrhea (16.7%), dizziness (16.7%), and palpitations (16.7%).

Study CBP-307CN002

This study is ongoing and there are no safety data available.

Study CBP-307CN003

This study is ongoing and there are no safety data available.

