2. OBJECTIVES AND ENDPOINTS

2.1. Objectives

The primary objective of the study is:

- To evaluate the effects of therapeutic and supratherapeutic CBP-307 plasma concentrations on the heart-rate corrected QT interval (QTc) in healthy subjects.

The secondary objectives of the study are:

- To demonstrate assay sensitivity of the study to detect a small QT effect using moxifloxacin as a positive control.
- To evaluate the safety and tolerability of therapeutic and supratherapeutic multiple oral doses of CBP-307 in healthy subjects.
- To assess the PK of CBP-307 following administration of therapeutic and supratherapeutic multiple oral doses in healthy subjects.
- To evaluate the effects of therapeutic and supratherapeutic multiple oral doses of CBP-307 on HR, PR and QRS intervals, and T-wave morphology.

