2.2.3. Safety Endpoints

The safety outcome measures for this study are as follows:

- incidence and severity of AEs
- incidence of laboratory abnormalities, based on hematology, clinical chemistry, and urinalysis test results
- 12-lead ECG parameters
- vital signs measurements.

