3. INVESTIGATIONAL PLAN

3.1. Overall Study Design and Plan

This will be a Phase I, randomized, double-blind, double-dummy, placebo-controlled, positive-controlled, multi-site, 3-arm study to investigate the effects of therapeutic and supratherapeutic oral doses of CBP-307 on the QTc interval in healthy male and female subjects.

Potential subjects will be asked to read and sign an informed consent form (ICF). After informed consent is obtained, screening procedures and tests to establish subject eligibility to enter the study will be performed within 28 days before Day 1. After informed consent has been obtained but prior to the initiation of study treatment administration, only SAEs will be reported. After placebo administration to all subjects on Day -1, all AEs, whether

volunteered, elicited, or noted upon physical examination, will be recorded throughout the study (ie, from Day -1 until the end of the study).

In this study, approximately 68 healthy subjects (at least 30% for each sex) will be randomized into 2 groups (Group 1 and 2) with 34 subjects in each. Group 2 consists of 2 sub-groups (Group 2A and 2B) and each sub-group will be randomized with 17 subjects. Randomized subjects will receive the assigned study drug as a single dose in the morning on Days 1, 2, 3 to 6, 7 to 15, and on Day 16 (placebo will be administered to all subjects on Day -1).

[figure not shown]
The following treatments will be administered:

- Starting doses of CBP-307 for titration (0.05 mg on Day 1 followed by an up-titrated dose of 0.1 mg on Day 2)
- A therapeutic dose of CBP-307 (0.2 mg, Days 3 to 6)
- A supratherapeutic dose of CBP-307 (0.5 mg, Days 7 to 15)
- Placebo (matched to moxifloxacin and CBP-307)
- Moxifloxacin (400 mg)

Moxifloxacin will be used as a positive control to determine the assay sensitivity of this study with an expected peak QT effect (placebo-corrected change-from-baseline QTcF; $\Delta\Delta\text{QTcF}$) of 10 to 15 msec.

An overview of the study design is shown in [Figure 1](#).

Figure 1: Study Schematic

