7.4.2. Clinical Laboratory Evaluations

Blood and urine samples will be collected for clinical laboratory evaluations at the times indicated in the Schedule of Assessments in [Appendix 6](#). Clinical laboratory evaluations are listed in [Appendix 2](#).

A serum qualitative pregnancy or urine test (females only) and follicle-stimulating hormone test (postmenopausal females only) will be performed at the timepoints specified in [Appendix 6](#). A positive urine pregnancy test will be confirmed with a serum pregnancy test. All pregnancies should be reported as specified in [Appendix 1](#).

Additional clinical laboratory evaluations will be performed at other times if judged to be clinically appropriate or if the ongoing review of the data suggests a more detailed assessment of clinical laboratory safety evaluations is required. At the discretion of the investigator, clinically significant clinical laboratory assessments may be confirmed by repeat sampling. If the clinical significance is confirmed, subjects will be excluded from participation or, if already included, will be followed until normalization of the test result or for as long as the investigator considers necessary.

Subjects will be asked to provide urine samples for drugs of abuse screen and cotinine test, and will undergo an alcohol breath test at the times indicated in the Schedule of Assessments in [Appendix 6](#). For all female subjects, a pregnancy test will be performed at the times indicated in the Schedule of Assessments in [Appendix 6](#).

An investigator (or designee) will perform a clinical assessment of all clinical laboratory data.

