Appendix 3: Total Blood Volume

The following blood volumes will be withdrawn for each subject.

Test	Volume per blood sample (mL)	Maximum number of blood samples	Total amount of blood (mL)
Clinical laboratory evaluations (including serology, syphilis, follicle-stimulating hormone, and serum pregnancy tests)	12.5	5	62.5
CBP-307/Moxifloxacin Pharmacokinetics (includes discard volume per draw)	8	41	328
Total:			390.5

If extra blood samples are required, the maximum blood volume to be withdrawn per subject will not exceed 500 mL.

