Appendix 6: Schedule of Assessments

Schedule of Assessments

Study Period	Screening	In-house Treatment Period													End-of- Study/Follow- up Visit
		-1	1	2	3 to 5	6	7 to 14	15	16	17	18	19	29±2		
Study Day(s)	-28 to -3 (or -5 if needed for COVID-19 testing) ¹	-2 (or -4 if needed for COVID-19 testing) ¹													
Informed consent	X														
Eligibility criteria review (Inclusion/Exclusion)	X	X													
Demographics	X														
Medical history	X														
Admission to clinical research unit ¹		X													
Discharge from clinical research unit ²													X		
Randomization				X											
Vital signs ^{3,8}	X	X	X	X	X	X	X	X	X	X	X	X			
Height/weight/BMI	X														
Physical exam	X	X												X	
Hematology	X	X					X						X	X	
Clinical chemistry (including cholesterol panel tests)	X	X					X						X	X	
Urinalysis	X	X											X	X	
Serology for HIV-1/HIV-2 antibodies and p24 antigen, HBsAb, HBcAb, HBsAg, or HCVAb		X													

Schedule of Assessments														
Study Period	Screening	In-house Treatment Period												End-of-Study/Follow-up Visit
Study Day(s)	-28 to -3 (or -5 if needed for COVID-19 testing) ¹	-2 (or -4 if needed for COVID-19 testing) ¹	-1	1	2	3 to 5	6	7 to 14	15	16	17	18	19	29±2
12-lead safety electrocardiogram ^{4,8}	X	X	X	X	X	X	X	X	X	X			X	X
Cardiac Telemetry Monitoring ⁹				X	X	X (Day 3)		X (Day 7)						
Breath alcohol, urine drug toxicology and cotinine	X	X												
Cardiodynamic monitoring (Holter)/replicate ECG extraction ⁵			X	X			X		X	X				
Pregnancy test ⁶	X	X												X
Follicle -stimulating hormone test (postmenopausal females only)	X													
CBP-307/placebo administration			X	X	X	X	X	X	X	X				
Moxifloxacin/placebo administration				X						X				
Blood sampling for PK ^{7,8}				X			X		X	X		X	X	
Adverse event monitoring	X	X	X	X	X	X	X	X	X	X	X	X	X	X
Concomitant medication recording	X	X	X	X	X	X	X	X	X	X	X	X	X	X

Abbreviations: BMI = body mass index; COVID-19 = Coronavirus Disease 2019; ECG = electrocardiogram; HBsAg = hepatitis B surface antigen; HCVAb = hepatitis C virus antibodies; HIV = human immunodeficiency virus; PK = pharmacokinetic.

1. Subjects will be asked to arrive at the clinical site in the afternoon 2 to 4 days before start of dosing on Day 1 (on Day -4 or Day -2 depending on the clinical site's requirements for COVID-19 testing).
2. Discharge from unit will occur after the 96-hour PK samples and after completion of safety assessments on Day 19.

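### No hematology, chemistry or urinalysis is scheduled while 0.5 mg is given (Days 7 to 15), although laboratory abnormalities are a safety endpoint and the safety objective covers the supratherapeutic dose

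*Protocol*

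**What the plan says.** All references are to the current protocol (Amendment 4, version 5.0).

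- **Objective (Section 2.1).** A secondary objective is "To evaluate the safety and tolerability of therapeutic and supratherapeutic multiple oral doses of CBP-307 in healthy subjects".
- **Endpoint (Section 2.2.3).** The safety outcome measures include "incidence of laboratory abnormalities, based on hematology, clinical chemistry, and urinalysis test results".
- **Dosing (Section 3.1).** Group 1 receives "A supratherapeutic dose of CBP-307 (0.5 mg, Days 7 to 15", after 0.2 mg on Days 3 to 6.
- **Schedule (Appendix 6).** Hematology and the row beginning "Clinical chemistry (including cholesterol panel tests" are marked at screening, check-in, Day 6, Day 19 and Day 29. Urinalysis is marked at screening, check-in, Day 19 and Day 29. All three rows are blank for Days 7 to 18.
- **Blood budget (Appendix 3).** The line "Clinical laboratory evaluations (including serology, syphilis, follicle-stimulating hormone, and serum pregnancy tests" allows at most five samples of 12.5 mL.
- **Unscheduled tests (Section 7.4.2).** "Additional clinical laboratory evaluations will be performed at other times if judged to be clinically appropriate", or if the ongoing data review points to a need for more detail.

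**The concern.** The objective names the supratherapeutic multiple-dose regimen, and the endpoint is an incidence of laboratory abnormalities. An incidence on 0.5 mg needs at least one planned measurement, in every subject, at a time when 0.5 mg exposure is present. The schedule has none. The two samples on either side are one before the escalation and one four days after the last dose. For urinalysis there is not even a 0.2 mg value.

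At stake is the laboratory part of the tolerability statement for the highest dose in the study. The highest repeated dose in the two completed studies summarised in Section 1.2.1.1 is 0.3 mg, so repeated 0.5 mg lies beyond that experience. It is also the segment with no laboratory sample. No analysis plan can recover samples that were not drawn.

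**Working it through.** **1. Is the table being read correctly?** The cells of each row were counted against the 14 day columns. Two rows with explanatory footnotes test the alignment:

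| Row | Marked days by count | Check |
|---|---|---|
| PK sampling | 1, 6, 15, 16, 18, 19 | agrees with footnote 7 (Days 1, 6, 15, 16, plus 72 and 96 h after Day 15) |
| Telemetry | 1, 2, 3, 7 | agrees with footnote 9 |
| Hematology, chemistry | screening, check-in, 6, 19, 29 | five samples |
| Urinalysis | screening, check-in, 19, 29 | no Day 6 |

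**2. Does the blood budget agree?** Appendix 3: 5 × 12.5 = 62.5 mL for laboratory tests, 8 × 41 = 328 mL for PK, total 62.5 + 328 = 390.5 mL, as stated there. The five laboratory samples are the five marked in Appendix 6, so no sample on 0.5 mg is budgeted elsewhere.

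**3. How large is the gap?** The 0.5 mg period has 15 − 7 + 1 = 9 dosing days. Scheduled laboratory samples in it: hematology 0, chemistry 0, urinalysis 0. From Day 6 to Day 19 is 13 days. The gap applies to all 34 subjects planned for Group 1.

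**4. What does Day 19 represent?** Day 19 is 96 h after the Day 15 dose (Appendix 6, footnote 2). Fraction remaining = 0.5^(96/t½), with half-lives from Section 1.2.1.2:

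- repeated dosing, 44 h: 0.22; 49 h: 0.26
- single dose, 25 h: 0.07 (23 h: 0.05; 29 h: 0.10)

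**5. How does that compare with the Day 6 sample?** Superposition of the planned doses (0.05 mg, 0.1 mg, 4 × 0.2 mg, 9 × 0.5 mg): A(t) = Σ Dᵢ × 0.5^((t − tᵢ)/t½). Assumptions: linear kinetics, one compartment, instantaneous input. Amounts are in mg.

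| t½ | Day 6, 6 h | Day 15, 6 h | Day 19 | Day 15 / Day 6 | Day 19 / Day 15 | Day 19 / Day 6 |
|---|---|---|---|---|---|---|
| 25 h | 0.332 | 0.870 | 0.072 | 2.62 | 0.08 | 0.22 |
| 44 h | 0.478 | 1.413 | 0.342 | 2.96 | 0.24 | 0.72 |
| 49 h | 0.506 | 1.544 | 0.432 | 3.05 | 0.28 | 0.85 |

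The Day 19 / Day 15 ratios are slightly above those in step 4 because they count from 6 h after the Day 15 dose (90 h, not 96 h). Against the Day 6 predose level, Day 19 is 0.37 (25 h), 1.05 (44 h) and 1.23 (49 h).

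Both samples taken after CBP-307 starts and before discharge therefore sit at roughly 0.2 mg exposure or below. Exposure on 0.5 mg is about 2.6 to 3.05 times the Day 6 level.

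**The case against.** **Sampling frequency is a design preference.** Section 2.2.3 ties the laboratory measure to no dose or day, and Appendices 3 and 6 agree with each other. The 0.5 mg period is covered by adverse event monitoring, vital signs, safety ECGs and Day 7 telemetry. This is fair, and it makes the matter a mismatch between aim and schedule rather than two conflicting statements. But none of those assessments measures a laboratory value.

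**Day 19 is not empty.** After nine 0.5 mg doses and with a 44 to 49 h half-life, exposure is still 0.72 to 0.85 times the Day 6 six-hour level. A persistent or delayed change could be seen. This stands: a reader might infer that supratherapeutic laboratory effects cannot be detected at all, and that would be too strong. The protocol gives no recovery time for any laboratory change, so how much would be missed is unknown.

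**Extra tests are allowed.** Section 7.4.2 provides for them on clinical grounds or when the data review suggests it. That protects individual subjects. Tests triggered by suspicion do not give an unbiased incidence.

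**The background data do not show worsening with dose.** In Study CBP-307CN001, at repeated 0.2 mg, neutrophil decreases occurred in 50% and ALT increases in 25%. At 0.3 mg the figures were 12.5% and 25%, and 16.7% of placebo subjects had increased transaminase. With eight subjects per active group this neither predicts a problem at 0.5 mg nor excludes one. The 0.2 mg rates should not be quoted alone.

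**Electrolytes and QT.** Because Inclusion Criterion 7 requires normal potassium, calcium and magnesium at screening and chemistry is not drawn near Day 15, a reader might infer that an unseen electrolyte shift threatens the QT result. The documents do not support this. Day 15 is compared with concurrent randomised placebo under the same confinement and diet, and a shift caused by the drug would already be part of the estimated ΔΔQTcF.

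**Conclusion.** The point holds as a mismatch between the safety objective and endpoint on one side and the schedule on the other. No laboratory sample is planned on any of the nine 0.5 mg days, and urinalysis is planned on no CBP-307 dosing day. Followed as written, the supratherapeutic laboratory assessment rests on a sample 96 h after the last dose, at about 22 to 26% of the Day 15 level (44 to 49 h half-life) or about 7% (25 h). Changes that arise and recover between Days 7 and 18 can be missed or understated.

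The schedule facts need no assumption beyond the column alignment, which was checked two ways. The exposure figures assume linear one-compartment kinetics and the protocol's half-lives. The consequence is confined to a descriptive safety endpoint; the primary QT and assay-sensitivity conclusions do not depend on it. It should be corrected because the correction is cheap.

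**What to change.** Reconcile Sections 2.1 and 2.2.3 with Appendix 6:

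- Add the existing hematology, chemistry and urinalysis set once within the 0.5 mg period, at a PK draw that is already scheduled and fasted. The Day 15 predose draw is one example; the exact day is for the sponsor. Section 6.2 already requires an overnight fast for PK days and for laboratory blood samples.
- Keep the Day 19 and Day 29 samples. Day 19 is the discharge sample and the only in-house laboratory sample after Group 2B receives moxifloxacin on Day 16.
- Update Appendix 3: six laboratory samples, 6 × 12.5 = 75 mL; total 390.5 + 12.5 = 403.0 mL. This respects the rule that "the maximum blood volume to be withdrawn per subject will not exceed 500 mL".

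The cost is one extra 12.5 mL sample at an existing venipuncture and one urine collection per subject, with subjects already in-house.

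If no sample is added, the protocol should say plainly that laboratory safety of the supratherapeutic dose is judged from a sample 96 h after the last dose, and the report should word its conclusion accordingly.

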This will be a Phase I, randomized, double-blind, double-dummy, placebo-controlled, positive-controlled, multi-site, 3-arm study to investigate the effects of therapeutic and supratherapeutic oral doses of CBP-307 on the QTc interval in healthy male and female subjects.

Potential subjects will be asked to read and sign an informed consent form (ICF). After informed consent is obtained, screening procedures and tests to establish subject eligibility to enter the study will be performed within 28 days before Day 1. After informed consent has been obtained but prior to the initiation of study treatment administration, only serious adverse events (SAEs) will be reported. After placebo administration to all subjects on Day -1, all adverse events (AEs), whether volunteered, elicited, or noted upon physical examination, will be recorded throughout the study (ie, from Day -1 until the end of the study).

In this study, approximately 64 healthy subjects (at least 30% for each sex) will be randomized into 2 groups (Group 1 and 2) with 32 subjects in each. Group 2 consists of 2 sub-groups (Group 2A and 2B) and each sub-group will be randomized with 16 subjects. Randomized subjects will receive the assigned study drug as a single dose in the morning on

Days 1, 2, 3 to 6, 7 to 15, and on Day 16 (placebo will be administered to all subjects on Day -1).

The following treatments will be administered:

- Starting doses of CBP-307 for titration (0.05 mg on Day 1 followed by an up-titrated dose of 0.1 mg on Day 2)
- A therapeutic dose of CBP-307 (0.2 mg, Days 3 to 6)
- A supratherapeutic dose of CBP-307 (0.5 mg, Days 7 to 15)
- Placebo (matched to moxifloxacin and CBP-307)
- Moxifloxacin (400 mg)

Moxifloxacin will be used as a positive control to determine the assay sensitivity of this study with an expected peak QT effect (placebo-corrected change-from-baseline QTcF; $\Delta\Delta QTcF$) of 10 to 15 msec.

Potential subjects will be screened to assess their eligibility to enter the study within 27 days prior to the first dose administration. Subjects will be admitted into the study site on Day -2 and will remain at the study site until discharge on Day 19. Treatment administration will occur on Days 1, 2, 3 to 6, 7 to 15, and 16 under fasting conditions (all subjects will receive placebo on Day -1). Continuous cardiodynamic electrocardiogram (ECG) monitoring and recording will begin at least 25 hours prior to the administration of study treatments on Day 1 and continue through 24 hours after the administration of study treatments on Days 1, 6, 15, and 16 and at corresponding timepoints on the day before dosing, ie, Day -1. Blood samples for PK analysis will be collected predose and at each postdose cardiodynamic ECG timepoint. Additional PK samples will be collected at 72 and 96 hours following dosing on Day 15. Subjects will return to the study site for a follow-up visit on Day 29±2 days.

Baseline for the primary analysis will be determined from predose timepoints collected for 25 hours on Day -1 (prior to administration of study treatments on Day 1). Continuous cardiodynamic monitoring (Holter) will be performed for 25 hours on Days -1, 1, 6, 15, and 16. The recording will be started 1 hour before dosing and at the corresponding clock time on Day -1. Replicate 12-lead ECGs will be extracted from the continuous recording prior to dosing (-30 minutes) and 0.5, 1, 2, 3, 4, 6, 8, 12, and 24 hours postdose on each day. Pharmacokinetic blood samples will be collected at the following timepoints: prior to dosing and 0.5, 1, 2, 3, 4, 6, 8, 12, and 24 hours after dosing on each PK sampling day (Days 1, 6, 15, and 16; sample collection windows are as follows: ±2 minutes for 0.5 hours postdose, ±5 minutes for 1 to 4 hours postdose, ±10 minutes for 6 to 8 hours postdose, and ±30 minutes for 12 to 24 hours postdose). Additional PK samples will be collected at 72 and 96 hours following dosing on Day 15 (sample collection window: ±30 minutes). Subjects will be inactive and in a supine position for at least 10 minutes prior to and 5 minutes after each cardiodynamic ECG extraction timepoint, which will end immediately prior to the PK sampling. At each timepoint, up to 10 ECG replicates will be extracted from a 5-minute time window (the last 5 minutes of the 15-minute period when the subject is maintained in a

supine, quiet position). The ECG effects of CBP-307 will be tested on data from Day -1 (baseline for both groups), Day 6 (therapeutic concentrations versus placebo), and Day 15 (supratherapeutic concentrations versus placebo). Assay sensitivity with moxifloxacin will be evaluated using ECG data collected on Days -1, 1, 15, and 16.

The central ECG laboratory (eResearch Technology Inc., Philadelphia, PA) will be blinded to treatment. The continuous 12-lead digital ECG data will be exported from the system and sent to the central ECG laboratory for review. Resting ECGs to be used in the analyses will be selected from predetermined timepoints specified above and will be read by the central ECG laboratory.

Safety assessments including AEs, vital signs, clinical laboratory tests, safety 12-lead ECGs, and physical examination findings will be performed at screening and at specific timepoints during the study, and/or at the follow-up visit. In addition, subjects will be monitored via cardiac telemetry at specific timepoints during the treatment period.

The total duration of study participation for each subject (from screening through follow-up visit) is anticipated to be approximately 59 days.

The start of the study is defined as the date the first subject signs an ICF. The point of enrollment occurs at the time of subject number allocation. The end of the study is defined as the date of the last subject's last assessment (scheduled or unscheduled).

Number of Subjects

Approximately 64 healthy subjects (at least 30% for each sex) will be randomized into 2 groups (Group 1 and 2) with 32 subjects in each. Group 2 consists of 2 sub-groups (Group 2A and 2B) and each sub-group will be randomized with 16 subjects.

Diagnosis and Main Criteria for Inclusion

Healthy male and female subjects aged between 18 and 60 years (inclusive) with a body mass index between 18.0 and 30.0 kg/m² (inclusive).

Investigational Medicinal Products, Dose, and Mode of Administration

The following treatments will be administered:

- Starting doses of CBP-307 for titration (0.05 mg on Day 1 titrated to 0.1 mg on Day 2; oral capsule)
- A therapeutic dose of CBP-307 (0.2 mg, Days 3 to 6; oral capsule)
- A supratherapeutic dose of CBP-307 (0.5 mg, Days 7 to 15; oral capsule)
- Placebo (matched to moxifloxacin, oral tablet and CBP-307; oral capsule)
- Moxifloxacin (400 mg; oral tablet).

Duration of Subject Participation in the Study

Duration of subject participation from the screening visit through follow-up visit will be up to approximately 26 days for screening period (Days -28 to -3), 21 days for the in-house treatment period (Days -2 to 19), and 10 ± 2 days for follow-up (Day 29 ± 2 days), in total approximately 59 days.

Endpoints

Electrocardiogram (Cardiodynamic):

The primary cardiodynamic endpoint is the change-from-baseline QTcF (Δ QTcF).

The secondary cardiodynamic endpoints are:

- Change-from-baseline HR, PR, QRS (Δ HR, Δ PR, and Δ QRS);
- Placebo-corrected change-from-baseline HR, QTcF, PR, and QRS ($\Delta\Delta$ HR, $\Delta\Delta$ QTcF, $\Delta\Delta$ PR, and $\Delta\Delta$ QRS);
- Categorical outliers for QTcF, HR, PR, and QRS;
- Frequency of treatment-emergent changes of T- wave morphology and U-wave presence.

Pharmacokinetics:

Blood samples will be collected for the analysis of plasma concentrations of CBP-307. The PK parameters of CBP-307 will be calculated using a model independent approach. The following PK parameter endpoints will be calculated: maximum observed concentration (C_{max}), area under the concentration-time curve from time zero extrapolated to infinity (AUC_{inf}), area under the concentration-time curve from time zero to 24 hours postdose (AUC_{0-24}), and time of the maximum observed concentration (t_{max}). Other noncompartmental parameters may be reported.

Safety:

Adverse events, clinical laboratory evaluations (hematology, clinical chemistry, urinalysis), 12lead ECGs, and vital signs measurements.

Statistical Methods

Cardiodynamic evaluation:

The primary analysis will be based on concentration-QTc modeling of the relationship between plasma concentrations of CBP-307 and change-from-baseline QTcF (Δ QTcF) with the intent to exclude an effect of placebo-corrected Δ QTcF ($\Delta\Delta$ QTcF) > 10 msec at clinically relevant plasma levels. Placebo-corrected Δ HR, Δ PR, Δ QRS, and Δ QTcF ($\Delta\Delta$ HR, $\Delta\Delta$ PR, $\Delta\Delta$ QRS, and $\Delta\Delta$ QTcF) will also be evaluated at each postdosing timepoint ('by-timepoint'

analysis). An analysis of categorical outliers will be performed for changes in HR, PR, QRS, QTcF, T-wave morphology, and U-wave presence. Assay sensitivity will be evaluated by concentration-QTc analysis of the effect on $\Delta\Delta$ QTcF of moxifloxacin using a similar model as for the primary analysis.

Pharmacokinetics:

The analyses will be carried out on the PK analysis population. All PK parameters will be presented by listings and descriptive summary statistics (mean, standard deviation, median, minimum, maximum geometric mean, and geometric coefficient of variation) separately by cohort. Individual and mean plasma CBP-307 and moxifloxacin concentration versus time data will be tabulated and plotted by dose level. Graphical displays of PK data may be provided as well.

Pharmacokinetic/electrocardiography analyses:

The relationship between CBP-307 plasma concentrations and the change from Δ QTcF will be evaluated using a linear mixed-effects modeling approach.

Safety:

All AEs will be listed and treatment-emergent AEs will be summarized using the descriptive methodology. Each AE will be coded using the Medical Dictionary for Regulatory Activities. Observed values for clinical laboratory test data, 12lead ECGs, vital signs, and physical examination findings will be listed.

TABLE OF CONTENTS

TITLE PAGE	1
SPONSOR APPROVAL	2
INVESTIGATOR AGREEMENT.....	3
INVESTIGATOR AGREEMENT.....	4
STUDY IDENTIFICATION	5
SYNOPSIS.....	7
TABLE OF CONTENTS.....	12
LIST OF TABLES AND FIGURES.....	15
LIST OF ABBREVIATIONS.....	16
1. INTRODUCTION	18
1.1. Disease Background.....	18
1.2. Overview of CBP-307.....	18
1.2.1. Summary of Clinical Experience	18
1.2.1.1. Safety	19
1.2.1.2. Pharmacokinetics	21
1.3. Overview of Moxifloxacin.....	22
1.4. Study Rationale.....	22
1.5. Benefit-risk Assessment.....	23
2. OBJECTIVES AND ENDPOINTS	23
2.1. Objectives	23
2.2. Endpoints	23
2.2.1. Electrocardiogram Endpoints.....	23
2.2.1.1. Primary.....	23
2.2.1.2. Secondary.....	23
2.2.2. Pharmacokinetic Endpoints	24
2.2.3. Safety Endpoints	24
3. INVESTIGATIONAL PLAN.....	24
3.1. Overall Study Design and Plan	24
3.2. Discussion of Study Design.....	27
3.3. Selection of Doses in the Study	27
4. SELECTION OF STUDY POPULATION	28
4.1. Inclusion Criteria	28
4.2. Exclusion Criteria	28
4.3. Subject Number and Identification	31
4.4. Subject Withdrawal and Replacement	31
4.5. Study Termination	32
5. STUDY TREATMENTS.....	32
5.1. Investigational Products.....	32

5.2.	Study Treatment Administration.....	34
5.3.	Randomization	34
5.4.	Blinding.....	35
5.5.	Treatment Compliance.....	35
5.6.	Drug Accountability.....	35
6.	CONCOMITANT THERAPIES AND OTHER RESTRICTIONS	36
6.1.	Concomitant Therapies	36
6.2.	Diet.....	36
6.3.	Smoking	37
6.4.	Exercise.....	37
6.5.	Blood Donation.....	37
